APPENDIX B: HAIR SPECIFIC SKINDEX-29 QUALITY OF LIFE QUESTIONNAIRE

Scoring:

Sx: Symptom (7-35), Em: Emotion (10-50), Fx: Function (12-60) Total Scoring = (29-145)

APPENDIX C: Physician's Global Assessment (PGA) Scoring and Subjective Scalp Hair Growth (SSHG) Evaluations

A Canfield stereotactic positioning device will be used for obtaining global photographs where the participant's chin and forehead are fixed, and on which a given camera and flash device are mounted to standardize the view, magnification and lighting at consecutive study visits. Participants will be asked to keep the same hair style and colour and the coordinators attempt to duplicate baseline hair parting and combing in subsequent follow-up visits. Two standard views (superior and vertex) will be taken at baseline, 8-, 16, and 26-weeks (Figure 5). The digital images will be graded. Paired baseline and post-treatment photographs will be evaluated by each site study doctor (at the Week 8, 16 & 26 follow up visits) in order to provide a physician global assessment (*sPGA*) score.

In addition, the photographs will then be independently reviewed by two blinded evaluators, to evaluate the independent physician's global assessment (iPGA)

The PGA score used is the standardized 7-point rating scale (-3 = greatly decreased, -2 = moderately decreased, -1 = slightly decreased, 0 = no change, +1 = slightly increased, +2 = moderately increased, +3 = greatly increased increased).

Figure 5. Global Photography, demonstrating fixation of the participant on a brow and chin rest with the camera mounted on a rotating arm.

Participants will be asked to assess subjective scalp hair growth (SSHG). They will be provided with the following questionnaire at each follow up visit (8, 16 and 26 weeks after baseline).

Subjective Scalp Hair Growth (SSHG)

1. Since the start of the study, I can see my bald spot getting smaller

Strongly Agree	Agree	No opinion either way	Disagree	Strongly Disagree
1	2	3	4	5

2. Because of the treatment I have received since the start of the study, the appearance of my hair is:

A lot better	Somewhat better	A little better	Same	A little worse	Somewhat worse	A lot worse
1	2	3	4	5	6	7

3. Ever since the start of the study, how would you describe the growth of your hair?

Greatly increased	Moderately increased	Slightly increased	No change	Slightly decreased	Moderately decreased	Greatly decreased
1	2	3	4	5	6	7

4. Ever since the start of the study, how effective do you think the treatment has been in slowing down your hair loss

Very effective	Somewhat effective	Not very effective	Not effective at all
1	2	3	4

5. Compared to the beginning of the study, which statement best describes your satisfaction with the appearance of:

a) The hairline front of your head?

Very satisfied	Satisfied	Neutral	Dissatisfied	Very Dissatisfied
1	2	3	4	5

b) The hair on top of your head?

Very satisfied	Satisfied	Neutral	Dissatisfied	Very Dissatisfied
1	2	3	4	5

c) Your hair overall?

Very satisfied	Satisfied	Neutral	Dissatisfied	Very Dissatisfied
1	2	3	4	5

APPENDIX D: TrichoScan Procedure for Hair Counts

REVIAN[®] Trial

1. PREFACE

This document describes in detail the methods that will be used to summarize and analyze the efficacy and safety data from protocol REV-01 (V6; August 22, 2018).

2. STUDY OBJECTIVES AND ENDPOINTS

The *REVIAN* device is a soft dome-shaped cap that contains integrated electronics and battery technology to control delivery of modulated light therapy (MLTTM) for a daily 10 minute treatment to treat androgenic alopecia (AGA) and promote hair growth in men and women. The cap contains a flexible printed circuit board (FPC), LEDs, printed circuit board assembly (PCBA), lithium-polymer battery, elastic fabric and foam fitting pieces. The cap is controlled and operated by a mobile app.

The primary objective of this study is to collect data on the safety and effectiveness of *REVIAN* in male and female participants with AGA through 26-weeks of treatment.

3. STUDY DESIGN

This study is designed as a prospective, randomized, controlled, double-blind, four-arm study. Up to 3 clinical sites will enroll up to 200 participants over an approximate 6-month duration. Eligible participants with AGA meeting all inclusion and exclusion criteria will be enrolled and randomized to one of four study arms in a 1:1:1:1 ratio:

- Arm 1: Active *REVIAN* 101 (___mW/cm² of 625 nm and 660 nm)
- Arm 2: Active *REVIAN* 102 (____mW/cm² of 425 nm)
- Arm 3: Active *REVIAN* 103 (____mW/cm² of 425 nm + ___mW/cm2 of 625 nm and 660 nm)
- Arm 4: Non-Active *REVIAN* Cap 100 (SHAM)

Male and female participants will be randomized from separate randomization schedules to ensure balance among treatment arms in each gender.

All data except for Global Assessment Photography and Macrophotography will be captured in an electronic clinical report form (eCRF). Global Assessment Photography and Macrophotography data will be imported from external vendor. Demographic, baseline characteristics, efficacy and safety data will be collected at regularly scheduled visits according to the planned schedule of procedures (Table 1).

Screening procedures will be performed at Visit 1.

Participants who are eligible to enroll will return within 7 days for Visit 2 to obtain baseline data and to be randomized to one of the treatment arms. The first treatment will be performed in the clinic on Visit 2.

Visit 3 will occur approximately 7 days later via telephone interviews to assess treatment compliance, to report use of concomitant medications and to report any adverse events.

Visits 4 and 5 will occur approximately 8 and 16 weeks, respectively, after Visit 1. Participants will return to the investigation centers for efficacy assessments and questionnaires.

The final visit (Visit 6) will occur approximately 10 weeks after Visit 5. Participants will undergo a final assessment of efficacy and safety at Visit 6. Participants will return the caps at Visit 6. If there are no adverse events requiring follow-up, participants will not need to return for any follow up assessments.

Any participant who competes the Week 16 efficacy assessments (at Visit 5) will be considered a completer.

Visit 1	Visit 2	Visit 3	Visit 4	Visit 5	Visit 6
Screening (Day -7)	Baseline (Day 0)	Phone Call (7 ±3 Days)	Week 8 ^{1,2} (56 ±5 Days)	Week 16 ^{1,2} (112 ±10 Days)	Week 26 ^{1,2} (182 ±10 Days)
X	Х				
X					
Х					
X					
X	Х				
X	Х				
	Х				Х
	Х				
	Х		Х3	X ³	X ³
	Х		Х	Х	Х
	Х	Х	Х	Х	Х
			Х	Х	Х
			Х	Х	Х
	Х		Х	Х	Х
	Х		Х	Х	Х
	Х		Х	Х	Х
		Х	Х	Х	Х
	Х	Х	Х	Х	Х
	Х	Х	Х	Х	Х
					Х
	Screening (Day -7) X X X X X X	Screening (Day -7) Baseline (Day 0) X X	Screening (Day -7) Baseline (Day 0) Phone Call $(7 \pm 3 Days)$ X X X	Screening (Day -7) Baseline (Day 0) Phone Call (7 ± 3 Days) Week 8 ^{1,2} (56 ± 5 Days) X X X X X X X X X X X X X X	Screening (Day -7) Baseline (Day 0) Phone Call (7 ±3 Days) Week 8 ^{1,2} (56 ±5 Days) Week 16 ^{1,2} (112 ±10 Days) X X X X X X X X X X X X X X X X X X X X X X X X X X X X X X X X X X X X X X X X X X X X X X X X X X X X X X X X X X X X X X X X X X X X X X X X X X X X X X X X

Table 1: Planned Visits and Procedures.

¹ All visit dates are in reference to Baseline, i.e., Visit 4 occurs about eight weeks (56 days) after the Baseline Visit.

² Participants will continue treatments throughout the 26-weeks with a daily 10-minute treatment for a total of 56 treatments over 8 weeks, 112 treatments over 16-weeks,

and 182 treatments over 26-weeks.

³ Participants may have tattoo ink reapplied to original site of ink dot application at these time periods.

⁴ SHG & PGA is not taken at baseline. These are assessed only at the follow up visits

4. SEQUENCE OF PLANNED ANALYSES

All analyses outlined in this document will be carried out after:

- The study database has been authorized by the PhotonMD Review team as complete and final;
- Protocol deviations that warrant exclusion from the per protocol analyses have been identified.

5. SAMPLE SIZE CONSIDERATIONS

Prior hair growth studies, regardless of potential efficacy of the Sham device, showed the delta between active treatments and control treatments was consistently at around 15-22 hairs/cm² which appears to be the expected level of improvement. It is estimated that participants in the active group will have increases of 15 hairs/cm² by 16-weeks. Assumptions are 15 hair count difference between treatments, standard deviation (SD)=20, 10% drop-out rate, 5% alpha level, 90% power and 2-sided t-test. Based on these assumptions, the study requires a minimum of 40 evaluable participants per arm.

The study will accrue a maximum of 200 participants (50 per each Active Study Arm and 50 control participants) to target, after lost to follow-up, a minimum of 160 evaluable (40 per arm) participants.

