5.2 Study Analysis, Sample Size and Pooling of Data

Study Analysis:

The primary efficacy analysis of this study is to compare the mean change in hair count change from baseline to 16-weeks following the initial application at baseline of REVIAN to the SHAM. This will be performed using mixed effects analysis of covariance (ANCOVA) where baseline characteristics and demographics may be considered as covariates. Comparison between active groups will not be tested for statistical significance as the study is not powered for these comparisons. Instead, each active will be compared to the SHAM individually. Details on adjustments for multiple testing to a single SHAM will be provided in a statistical analysis plan.

Power Calculation, Sample Size:

Prior hair growth studies, regardless of potential efficacy of the SHAM device, showed the delta between active treatments and control treatments was consistently at around 15-22 hairs/cm² which appears to be the expected level of improvement. It is estimated that participants in the active group will have greater than 15 hairs/cm² by 16-weeks. The study design is a parallel arm study of superiority of PhotonMD devices to SHAM with a minimum of 40 participants per arm. Assumptions are 15 hair difference between treatments, standard deviation (SD)=20, 10% dropout rate, 5% alpha level, 90% power and 2-sided t-test.

The study will accrue a total of 200 participants (50 per each Active Study Arm and 50 control participants) to make sure, after lost to follow-up, that there is a minimum of 160 evaluable (40 per arm) participants.

Pooling of Data:

The clinical study will be conducted under a common protocol for each of 3 investigational sites with the intention of pooling the data over all sites for analysis. Every effort will be made to promote consistency in study execution at each investigational site.

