8.2. Hypothesis Testing

The treatment consists of 3 active caps and one Sham cap. Each active cap group will be compared to the same Sham group using 1 degree of freedom contrasts in general linear models analysis of covariance (ANCOVA). Comparisons will be adjusted for multiple comparisons to the same Sham group using Dunnett's correction.

The primary outcome is the change from baseline in hair count after 16 weeks of treatment with a cap. The null hypothesis is there is no difference in outcome between an active cap compared to a Sham cap, while the alternative hypothesis is there is a difference outcome between active compared Sham cap:

 H_{null} : $D_{active} = D_{Sham}$

 $H_{alternative} \text{: } D_{active} \neq D_{Sham}$

The null hypothesis will be rejected in favor of the alternative hypothesis for each active cap if the Dunnett's corrected p-value for the contrast ≤ 0.05 . Treatment superiority will be

demonstrated if the significant difference is in favor of the active cap (e.g., greater increase in hair count for the active cap. No comparisons between active caps will be performed.

Secondary outcomes will the same hypotheses testing process as the primary outcome, but with statistical methods appropriate for the type of endpoints to be tested. For example, continuous outcomes will be analysed by parametric methods, such as ANCOVA, while categorical outcomes will be analysed by non-parametric methods, such as Cochran-Mantel-Haenszel (CMH) test. Details of analyses by outcomes are provided in Section 10.

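### The 90% power stated for 40 evaluable participants per arm is for an unadjusted 5% t-test; under the SAP's Dunnett-adjusted primary test it is about 84% per cap

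*Combined protocol and SAP*

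**What the plan says.** SAP section 5 gives the planning inputs: "Assumptions are 15 hair count difference between treatments, standard deviation (SD)=20", with "10% drop-out rate, 5% alpha level, 90% power and 2-sided t-test". It then states: "Based on these assumptions, the study requires a minimum of 40 evaluable participants per arm". Protocol section 5.2 uses the same inputs and plans 200 participants, 50 per arm, so "that there is a minimum of 160 evaluable (40 per arm) participants" after loss to follow-up. In the SAP, 200 is a maximum. Neither sample size text mentions an adjustment for testing three caps.

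On multiplicity, protocol section 5.2 says that each active cap is compared with sham individually, and then: "Details on adjustments for multiple testing to a single SHAM will be provided in a statistical analysis plan". SAP section 8.2 supplies the detail: "Comparisons will be adjusted for multiple comparisons to the same Sham group using Dunnett's correction". The null hypothesis for a cap is rejected only if its Dunnett-corrected p-value is at most 0.05. The example code in SAP section 10.1 requests the same adjustment.

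**The concern.** The power statement and the decision rule belong to different tests. The protocol left the multiplicity adjustment open, and the SAP settled it but carried the sample size paragraph over with its unadjusted 5% t-test. A Dunnett comparison of three caps with one control needs a larger test statistic than a single t-test, so power at the same number per arm must be lower than stated.

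Each cap receives its own verdict, so power per cap is the figure a reader needs when a cap is not significant. As written, such a result would be judged against a 10% chance of missing a true 15-hair effect. At the stated minimum evaluable size that chance is about 16%.

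**Working it through.** **Inputs.** Difference 15 hairs/cm², SD 20, two-sided 5%, 90% power, 10% dropout, minimum 40 evaluable per arm, up to 50 per arm enrolled (SAP section 5). Four equal arms (SAP section 3). Dunnett adjustment for three comparisons with one sham (SAP sections 8.2 and 10.1).

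**Step 1: reproduce the plan's figure.** By the normal approximation,

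n per arm = 2 × (1.960 + 1.282)² × 20² / 15² = 37.4, so 38.

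The exact noncentral t calculation gives 90.5% power at 39 per arm and 91.2% at 40. The stated 40 per arm for 90% power is therefore the unadjusted single-comparison figure.

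**Step 2: critical value of the planned test.** With three comparisons against one control, equal arms (correlation 0.5 between contrasts) and 4 × (40 − 1) = 156 degrees of freedom, numerical integration gives a two-sided Dunnett critical value of |t| = 2.372. This is a per-comparison two-sided alpha of 0.0189.

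**Step 3: power per cap at 40 per arm.** The noncentrality parameter is

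15 / (20 × √(2/40)) = 3.354.

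A quick check by the normal approximation is Φ(3.354 − 2.372) = Φ(0.982), about 83.7%. The exact noncentral t value is 83.6%. A simulation at 40 per arm gave a familywise error of 5.0% under the null and 83.5–83.6% power per cap.

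**Step 4: other sizes under Dunnett's test.**

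| Evaluable per arm | Power per cap |
|---|---|
| 40 (stated minimum) | 83.6% |
| 45 (50 less 10%) | 88.1% |
| 47 | 89.6% |
| 48 | 90.3% |
| 50 (no loss) | 91.6% |

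Holding 40 per arm, 90% power needs a difference of 16.4 hairs, or an SD of 18.3 or less.

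**Step 5: dropout.** 40 / 0.9 = 44.4, so 10% dropout calls for 45 per arm to keep 40. Going from 50 to 40 is 1 − 40/50 = 20%. This does not affect the 83.6%, but it decides which row of the table describes the expected trial.

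**The case against.** The arithmetic is not in dispute. The case on the other side is that 84% is a floor and that several features of the plan could raise it.

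- **40 is a minimum.** With 50 enrolled and the plan's own 10% dropout, 45 remain and the shortfall is about 2 points. This stands, and the restatement should give both figures. But the plan attaches 90% to 40 evaluable, and even 45 does not reach it.
- **The primary analysis is ITT with carried-forward values** (SAP section 8.1), so up to 50 per arm enter it, nominally 91.6%. That holds only if imputation leaves the 15-hair effect and the SD intact. A participant without a week 8 visit is assigned zero change, which dilutes a true gain. An illustrative simulation with 50 per arm gives about 87–88% at 10% dropout and about 83% at 20%. It assumes linear growth, no sham change and dropout split evenly before and after week 8. Those assumptions are not in the documents, and the 20% figure moves by a point or two with the SD assumed at week 8.
- **Covariates in the ANCOVA could reduce residual variance.** If SD 20 is the unadjusted SD, a covariate correlation of about 0.40 would restore 90% at 40 per arm; 0.30 gives 87.2%. The documents give no correlation, and SAP section 8.3 selects covariates by a p < 0.10 screen, so this cannot be credited. It is fair that 83.6% takes no account of covariates, and the text should say so.
- **15 hairs is the low end of the cited 15–22 range.** At 18.5 hairs, power at 40 per arm is 96%. But 15 is the effect to which the plan ties its 90%.
- **50 per arm may be 45 plus a margin.** Possibly; neither document says how 50 was derived. This is a reason to explain the figure, not to leave it.
- **90% might mean at least one cap.** If all three caps gain 15 hairs, that probability is about 96% (about 67% for all three). The inputs reproduce the per-comparison figure, and SAP section 8.2 judges each cap separately.

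**Conclusion.** The concern holds. On the plan's own inputs, 90% power at 40 evaluable per arm belongs to an unadjusted t-test that the trial will not use. Under the Dunnett rule, power per cap is 83.6% at 40 per arm, about 6 points below the claim. It is 88.1% at 45 per arm, about 2 points below.

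These figures assume a 15-hair difference, a common SD of 20, equal arms, a pooled error term and no gain from covariates. Dunnett's procedure is a suitable choice and controls the familywise error, so the fault lies in the power statement and not in the test. The dropout mismatch is a separate, smaller inconsistency.

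**What to change.** In SAP section 5 and protocol section 5.2, replace the power statement with wording such as: *With 40 evaluable participants per arm, a 15-hair difference and SD 20, power for each active-versus-sham comparison under Dunnett's two-sided 5% test is about 84% (88% at 45 per arm), without allowance for covariate adjustment.*

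In the same paragraphs, either state that 50 per arm allows for 20% loss down to 40, or keep 10% and state that it leaves 45 per arm.

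The cost is wording in two places and a less favourable stated power. No extra enrolment is needed for this correction. If the sponsor wished to keep 90% per cap, 48 evaluable per arm would be required. At 10% dropout that is 48 / 0.9 = 53.3, so 54 per arm and 216 in all, which exceeds the 200 maximum.

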6. ANALYSIS POPULATIONS

Participants receive either an active *REVIAN* Cap or a non-active *REVIAN* Cap (three versions of an active *REVIAN* Cap and one non-active *REVIAN* Cap). The following participant groups or analysis populations will be used to complete the analysis of data:

Intent-to-Treat participant population (ITT): The ITT participant population will include all participants that started a treatment at Baseline. All baseline characteristics, demographics and primary efficacy analyses will be performed on the ITT population.

Per-Protocol participant population (PP): The PP participant population will include all participants in the ITT population with 16-week follow-up data, with no major protocol deviations and at least 80% compliance. The primary and secondary efficacy analyses also will be performed on the PP population.

Safety participant population (SAF): The SAF is the same as the ITT population. All safety summaries will be performed on the SAF population.

7. INTERIM ANALYSES

No interim analyses are planned for this study.

8. GENERAL CONSIDERATIONS FOR DATA ANALYSES

The purpose of the study is to collect data on the safety and effectiveness of *REVIAN* in participants with AGA. In general, for continuous variables, the sample size, mean, standard deviation, minimum and maximum will be presented. For categorical variables, the number and percentage in each category will be presented. All statistical analyses will be performed using SAS version 9.4 for PC. Unless otherwise specified, statistical significance will be determined using p ≤ 0.05 .

All outcomes will be provided in listings by participant and treatment group. In addition, some endpoints will be summarized in tables by treatment group.

Primary Efficacy Endpoint: The primary efficacy endpoint of this study is the change in hair count from baseline to 16-weeks following the initial application (CFB HC16).

Primary Safety Endpoint: The primary safety outcome will be determined by evaluating by the type, frequency, severity, and relatedness of adverse events through the 16-week period for all participants.

Secondary Efficacy Endpoints:

Change from Baseline Hair Count: Like the primary endpoint, change from baseline hair count, will also be assessed at 8 (CFB_HC08) and 26 (CFB_HC26) weeks.

Rate of Change in Hair Growth: The rate of change in hair growth at 8, 16, and 26 weeks will be calculated as a ratio of change from baseline to baseline.

Independent Physician's Global Assessment (iPGA): Two independent reviewers will assess overall hair growth from photographs, using PGA scores at weeks 8, 16 and 26. The PGA score hair growth as: -3=greatly decreased, -2=moderately decreased, -1=slightly decreased, 0=no change, 1=slightly increased, 2=moderately increased and 3=greatly increased. In the event the two independent reviewers do not agree, a third assessment will be made by the PI. The PI's score will superceed the two other independent reviewers' score.

Site Physician's Global Assessment (sPGA): The site investigator will assess overall hair growth using the PGA scores at weeks 8, 16 and 26.

Subjective Scalp Hair Growth Score (SHG): Beginning at Week 8, participants will complete a subjective hair growth questionnaire. The participants choose the answer that best fits the following statements:

- 1) Since the start of the study, I can see my bald spot getting smaller. (1="strongly agree" to 5="strongly disagree")
- 2) Because of the treatment, I have received since the starts if the study, the appearance of my hair is: (1="a lot better" to 5="a lot worse")
- 3) Ever since the start of the study, how would you describe the growth of your hair? (1="greatly increased" to 7="Greatly decreased")
- 4) Ever since the start of the study, how effective do you think the treatment has been in slowing down your hair loss? (1="Very effective" to 4="Not effective at all")
- 5) Compared to the beginning of the study, which statement best describes your satisfaction with your appearance of:
 - a. The hairline in front of your head? (1="very satisfied" to 5="very dissatisfied")
 - b. The hair on top of your head? (1="very satisfied" to 5="very dissatisfied")
 - c. Your hair overall? (1="very satisfied" to 5="very dissatisfied")

SHG will be administered at 8 weeks, 16 weeks and 26 weeks

Hair Specific Skindex-29 Quality of Life Questionnaire (HSSQOL): The hair specific skindex-29 QOL questionnaire is a 29-item questionnaire with 3 domains: 7 questions for symptoms domain, 10 questions for emotion domain and 12 questions for function domain. Participants score each question on a scale from 1 (never) to 5 (all the time). Total scores will be summed at Week 8, 16 and 26. HSSQOL will be administered at baseline, 8, 16 and 26 weeks.

Secondary Safety Endpoint: The secondary safety outcome will be determined by evaluating by the type, frequency, severity, and relatedness of adverse events through the 26-week period for all participants.

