	 Severity (Mild, Moderate, Severe) Seriousness (Serious, Non-serious) Device-Relatedness (Unrelated, Probably Related, Possibly Related, Definite) Procedure-Relatedness (Unrelated, Probably Related, Possibly Related, Definite) 					

Study Duration	Study enrollment will be completed over approximately 7-months. All participants included in this clinical investigation will be evaluated for safety and efficacy at 8-, 16- and 26-weeks. The primary study endpoint will be evaluated at 16-weeks and secondary endpoints will be evaluated at 8-, 16- and 26-weeks.
	The total duration of the enrollment period and completion of the 26-week endpoint is approximately 54-weeks (Approx. 13.5 months) for primary and secondary endpoint evaluation.

PRINCIPAL CONTACTS

	Name, Address and Contact
Study - Principal Investigator	
Study Sponsor/Monitor	
Study Statistician	
Terminal Hair Count and Macro- Photographic Independent Reviewer	
Medical Monitor	
Official Commercial Correspondent	

ABBREVIATIONS AND TERMS

Table 1. Abbreviations and Terms

AE	Adverse Event
AGA	Androgenetic Alopecia
ANCOVA	One-way Analysis of Covariance
ССО	Cytochrome C Oxidase
CRF	Case Report Form
DHT	Dihydrotestosterone
FDA	Food and Drug Administration
FPHL	Female Pattern Hair Loss
FPCB	Flexible Printed Circuit Board
GCP	Good Clinical Practice
HF	Hair Follicles
HREC	Human Research Ethics Committee
ICF	Informed Consent Form
IFU	Instructions for Use
ITT	Intent-to-Treat
ISO	International Organization for Standardization
IRB	Institutional Review Board
LED	Light Emitting Diode
LOCF	Last Observation Carried Forward
LLLT	Low-Level Laser Light Therapy
LTFU	Lost to Follow up
MDD	Medical Device Directive
MLT	Modulated Light Therapy
MPHL	Male Pattern Hair Loss
NO	Nitric Oxide
PCB	Electronically Controlled Circuit Board
PHI	Personal Health Information
PGA	Physician Global Assessment Score
PI	Principal Investigator
РР	Per-Protocol Patient Population
QOL	Quality-of-Life
SAE	Serious Adverse Event
SD	Standard Deviation
SSHG	Subjective Scalp Hair Growth
UADE	Unanticipated Adverse Device Effect

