2.2 Study Design Overview

This study is designed as a prospective, randomized, controlled, double-blind, four-arm study. Up to 4 clinical sites will enroll up to 200 participants over an approximate 7-month duration. Eligible participants with AGA meeting inclusion and exclusion criteria will be enrolled and randomized to one of four study arms.

```
      Study Arm 1: Active REVIAN 101 (_____ mW/cm^2 of 625 nm and 660 nm)

      Study Arm 2: Active REVIAN 102 (_____ mW/cm^2 of 425 nm)

      Study Arm 3: Active REVIAN 103 (____ mW/cm^2 of 425 nm + ____ mW/cm2 of 625 nm and 660 nm)

      Study Arm 4: Non-Active REVIAN (SHAM) Cap 100
```

The outcome measures in this study will include the following:

- Quantitative Scalp Hair Growth (Macrophotography of 1-cm² area of interest)
- Subjective Scalp Hair Growth (SSHG) score
- Physician's Global Assessment (PGA) score
- Hair Specific Skindex-29 Quality of Life Score Questionnaire

All participants will be asked to complete self-administering scalp hair growth and life quality questionnaires at each follow-up visit. Investigators will be required to complete global assessments of scalp hair growth for each enrolled participant at each follow-up visit.

Macrophotography evaluations will be performed at baseline, 8-, 16-, and 26 weeks for all participants. Global photographs of superior and vertex scalp will be taken by the PI to be assessed by a blinded reviewer once all photos have been captured for each participant per visit.

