3.3 Blinding Procedure

The participants, Principal Investigator and Study Coordinators will be blinded to treatment, except in the case of an emergency that requires unblinding of a participant. In order for each Principal Investigator to remain blinded for all participants throughout the study, each site will designate a minimum of one, but no more than two, licensed members of the study staff (e.g., M.D., D.P.M., P.A., Nurse Practitioner, study assistant, etc.) to be the unblinded Treatment Administrator. The role of the Treatment Administrator(s) will be to administer the study device (both active and SHAM) and maintain and complete the Device Treatment and Training logs. In order to verify that the correct application was being used for each participant at each study visit, the code will be reviewed by the local Study Sponsor during monitoring visits and throughout the study when a participant is enrolled.

Each participant will register their user name in the mobile app and run an application for the first treatment prior to leaving the clinic. The Principal Investigator and/or designated Sub-Investigators will serve as the blinded evaluators for all study visits.

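### SAP 8 lets a PI, site or study level not specified, replace both independent reviewers' iPGA scores on any disagreement, and nothing stops that PI being the same participant's sPGA rater

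*Combined protocol and SAP*

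**What the plan says.** **The iPGA rule.** SAP section 8 has two independent reviewers score the photographs at weeks 8, 16 and 26 on the scale from -3 to +3. It then adds: "In the event the two independent reviewers do not agree, a third assessment will be made by the PI". The next sentence reads: "The PI's score will superceed the two other independent reviewers' score". No size of disagreement is stated. The protocol has no adjudication step for iPGA.

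**The two assessments.** Protocol Appendix C gives sPGA to the site: "Paired baseline and post-treatment photographs will be evaluated by each site study doctor" at the follow-up visits. After that, "the photographs will then be independently reviewed by two blinded evaluators", which yields iPGA. Both scores therefore come from the same images, and sPGA comes first.

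**Who the PI is.** Protocol Table 1 expands the abbreviation as Principal Investigator. The Principal Contacts table has a "Study - Principal Investigator" row, which is a study-level role. Protocol 3.3 uses the title at site level ("In order for each Principal Investigator to remain blinded for all participants throughout the study") and adds: "The Principal Investigator and/or designated Sub-Investigators will serve as the blinded evaluators for all study visits". Protocol 2.2 says: "Global photographs of superior and vertex scalp will be taken by the PI to be assessed by a blinded reviewer". Protocol 3.4.2 places the first treatment at the PI's office.

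**Number of reviewers.** The Protocol Summary, 2.2, 2.4.2 and 5.1 speak of one reviewer. Appendix C and SAP 8 speak of two.

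**The concern.** The plan keeps iPGA and sPGA as separate secondary endpoints with separate tables (14.2.4 and 14.2.5). The value of iPGA is that it comes from readers outside the site. The SAP rule hands the final score to the PI whenever the two outside readers differ, with no tolerance and no majority or median rule. If that PI is the investigator who already scored the participant for sPGA, part of the independent endpoint may be the site's own rating used again. Similar results on iPGA and sPGA could then not be read as confirmation by a separate reader. What is at stake is how one secondary endpoint is interpreted.

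**Working it through.** **Step 1: the passages side by side.**

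| Question | What the documents give |
|---|---|
| What triggers the third read? | Any non-agreement (SAP 8) |
| What does it do? | Replaces both scores, whether or not it matches either (SAP 8) |
| Which PI? | Not stated in the SAP. Study level in Principal Contacts; site level in protocol 3.3, 2.2 and 3.4.2 |
| Who gives sPGA? | The site investigator (SAP 8) or site study doctor (Appendix C); under 3.3 the PI and/or Sub-Investigators evaluate at visits |
| Must the adjudicator differ from the sPGA rater? | No such rule |
| Must the adjudicator be masked to sPGA? | No such rule |
| Is the PI blinded to treatment? | Yes, as planned (3.3) |

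The protocol's working uses of PI are at site level, so a site PI is the natural reading, though not a settled one. Under that reading the overlap with the sPGA rater is possible and unguarded.

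**Step 2: how many scores the PI could set.** The documents give no agreement rate, so there is no figure of the plan's own to reproduce. The PI-set share is 1 minus exact agreement. For an assumed agreement of 40% to 90%, the share is 60% down to 10%. Of 40 evaluable participants per arm, that is 24 down to 4 at each visit.

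**Step 3: what the overlap could do (illustration only).** Assumptions: true score normal with mean 0.7 and SD 1 category; each read adds independent normal error with SD s; scores are rounded and clipped to -3..+3; 2,000,000 draws. Under the SAP rule,

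P(iPGA = sPGA) = A + D × m,

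where A is the chance that the reviewers agree and their common score equals sPGA, D is the chance that they differ, and m is the chance that the PI's score equals sPGA when they differ.

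| s | 0.2 | 0.4 | 0.5 | 0.7 |
|---|---|---|---|---|
| D (PI sets the score) | 0.224 | 0.429 | 0.507 | 0.618 |
| Reviewers differ by more than one category | <0.001 | 0.017 | 0.048 | 0.139 |
| PI matches neither reviewer, given D | 0.00 | 0.08 | 0.16 | 0.31 |
| iPGA = sPGA, separate sPGA rater | 0.809 | 0.614 | 0.528 | 0.402 |
| iPGA = sPGA, same PI, fresh read | 0.81 | 0.61 | 0.53 | 0.40 |
| iPGA = sPGA, same PI for everyone, score repeated (m = 1) | 0.888 | 0.803 | 0.787 | 0.788 |

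At s = 0.5 the repeat case gives A = 0.787 − 0.507 = 0.280. The fresh-read case then implies m = (0.528 − 0.280) / 0.507 = 0.489. Moving m from 0.489 to 1 accounts for the whole rise, 0.507 × 0.511 = 0.259.

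The fresh-read row equals the separate-rater row because the model gives every read independent error, whoever makes it. In practice one person's two reads are probably correlated, which would place the result between the two bounds.

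Partial overlap gives less. If the PI rates sPGA for half of the participants (one site at its cap of 100 of 200, protocol 2.5) and repeats each score, the value at s = 0.5 is 0.657.

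**The case against.** The strongest case for the plan has four parts.

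- **The PI is defined and blinded.** Table 1 expands the abbreviation, and only the level is open. The study-level contact entry has had personal data removed, so the documents cannot show whether that person rates participants. If the study PI is meant and rates no one, the overlap disappears. Under the site reading, protocol 3.3 still allows a Sub-Investigator to do the visit evaluations.
- **A third read is a legitimate, pre-specified rule.** SAP 8 calls for a third assessment, not for the sPGA score to be copied.
- **No analysis relies on concordance.** SAP 10.2 compares each endpoint with Sham separately and plans no iPGA–sPGA agreement analysis.
- **The reviewer count is a consistency matter.** Appendix C and the SAP agree on two.

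All four points stand and limit the finding, but they do not remove it. A pre-specified adjudicator can still be the wrong person for an endpoint labelled independent, and no text excludes the sPGA rater.

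A reader might infer two stronger things. One is that iPGA largely duplicates sPGA, in some 79% to 89% of participants. That figure needs the PI to rate everyone on both measures and to repeat each score, and no passage says either. The other is that the override biases iPGA towards the active caps. Protocol 3.3 plans for the PI to be blinded, and nothing in the documents shows a direction of error by arm.

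**Conclusion.** The concern holds as a gap in independence. SAP 8 gives the final iPGA score to a PI of unspecified level on any disagreement. The protocol points to a site PI, and neither the overlap with the sPGA rater nor knowledge of the sPGA score is prevented. The share affected is unknown.

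Under the stated assumptions the effect runs from none (fresh reads: 81/61/53/40%, the same as with a separate rater) to an upper bound of 89/80/79/79%. These figures rest wholly on the assumed reader error and show scale only. The consequence is confined to how one secondary endpoint is read. No treatment bias is shown and the primary hair-count analysis is unaffected. The fix is cheap enough that the plan should make it.

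**What to change.** - **SAP 8:** replace the PI as adjudicator with *a blinded investigator who did not give that participant's sPGA and is masked to it (for example, an investigator from another site)*. Keep the integer scale and the modified-ridit CMH test in SAP 10.2.
- **Reporting:** give the number of adjudicated iPGA scores by arm and visit.
- **Consistency:** reconcile the one-reviewer wording (Protocol Summary, 2.2, 2.4.2, 5.1) with the two-reviewer wording (Appendix C, SAP 8).

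**Cost.** A change to SAP 8, one reporting line and matching protocol edits. The third read is already planned and the study has several sites, so no staff need be added. The downside is sending discordant photographs to another site's investigator.

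**Option, not required.** Averaging the two blinded reads would also remove the overlap, but it changes the scale. Under the same assumptions, 22% to 49% of scores become half-points, and pairs more than one category apart (up to about 14%) go unadjudicated. The share scoring at least 2 falls from 21–25% to 17–18%.
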